Adverse events and clinical laboratory tests will be collected at every visit and summarized through Week 144. Additionally, summaries of AEs, discontinuations due to AEs, and laboratory data including BMD measurements (via DXA scans, serum creatinine and creatinine clearance by Cockcroft-Gault) by original treatment arms (TAF versus TDF) will continue through Week 384. Fracture risk assessment will be evaluated at Baseline. In China, this fracture risk assessment will be evaluated at sites with DXA capability only.

Efficacy:

The primary efficacy endpoint is the proportion of subjects with plasma HBV DNA levels below 29 IU/mL at Week 48.

Other secondary efficacy endpoints are:

- The proportion of subjects with plasma HBV DNA < 29 IU/mL at Weeks 96, 144, 240, and 384
- The proportion of subjects with plasma HBV DNA < 29 IU/mL (target not detected) at Weeks 48, 96, 144, 240, and 384
- The proportion of subjects with ALT normalization (by central laboratory and American Association for the Study of Liver Diseases [AASLD] criteria) at Weeks 48, 96, 144, 240, and 384
- The proportion of subjects with HBsAg loss at Weeks 48, 96, 144, 240, and 384
- The proportion of subjects with HBsAg seroconversion to anti-HBs at Weeks 48, 96, 144, 240, and 384
- The change from baseline in fibrosis as assessed by FibroTest[®] at Weeks 48, 96, 144, 240, and 384
- The incidence of drug resistant mutations at Weeks 48, 96, 144, 240, and 384

Pharmacokinetics:

The following TAF and TFV plasma pharmacokinetic parameters will be calculated for the substudy population (n = 30):

C_{max} , T_{max} , C_{last} , T_{last} , C_{tau} , AUC_{tau} , AUC_{last} , CL/F , V/F , λ_z and $t_{1/2}$

Single PK plasma samples collected at Weeks 4-48 may be used for estimation of population pharmacokinetics of TAF and TFV.

Single PBMC samples at selected PK substudy sites collected at the intensive PK substudy visit will be used for TFV-DP concentration determination

Statistical Methods:

The primary analysis will be performed when approximately 390 subjects complete 48 weeks of the double-blind treatment period or discontinue prematurely. The analysis will compare the TAF arm to the TDF arm.

Analysis Methods:

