The current study is designed to evaluate non-inferiority of TAF compared to TDF in regard to the proportion of subjects with HBV DNA levels below 29 IU/mL at Week 48. The durability of TAF compared to TDF in regard to the proportion of subjects with HBV DNA < 29 IU/mL at Weeks 96 and 144 will also be assessed in a double blind fashion. In addition to treatment naïve subjects, treatment experienced CHB subjects who are viremic and with elevated ALT levels at screening are included. This is based on given results from GS-US-174-0106 (ADV suboptimal responders) and GS-US-174-0121 (LAM-resistant subjects) which demonstrated in viremic patients comparable rates of HBV DNA suppression, as described below, in comparison to results in mostly treatment naïve subjects participating in pivotal studies GS-US-174-0102 (HBeAg-negative subjects) and GS-US-174-0103 (HBeAg-positive subjects). Given the unique properties of TAF (efficient delivery of the active moiety, TFV-DP, to HBV-infected hepatocytes with reduced systemic TFV exposures), this study will also evaluate the potential safety differences (e.g. renal- and bone-related complications) of TAF relative to TDF at Week 48 and long term comparative safety at Week 96 and 144, after which subjects will be further evaluated for longer-term safety and efficacy of TAF in an open-label TAF 25 mg QD extension phase through Week 384. The extension phase is important as it will enable the evaluation of subjects treated for the entire 384 week period with TAF as well as those who received 144 weeks of TDF initially in a double-blinded fashion followed by an additional 240 weeks of open-label TAF. The latter group will allow an ongoing assessment, including possible resolution, of any potential bone- and/or renal-related (or other) complications during TAF treatment that might have arisen under initial treatment with TDF.

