2. OBJECTIVES

The primary objectives of this study are:

- To compare the efficacy of tenofovir alafenamide (TAF) 25 mg QD versus tenofovir disoproxil fumarate (TDF) 300 mg QD for the treatment of HBeAg-negative, chronic hepatitis B at Week 48 in treatment-naïve and treatment-experienced subjects. The primary efficacy parameter is the proportion of subjects with plasma HBV DNA levels below 29 IU/mL
- To compare the safety and tolerability of TAF 25 mg QD versus TDF 300 mg QD for the treatment of HBeAg-negative, chronic hepatitis B at Week 48 in treatment naïve and treatment experienced subjects

The key secondary safety objectives of the study are:

- To compare the safety of TAF 25 mg QD versus TDF 300 mg QD as determined by the percent change from baseline in hip and spine BMD at Week 48
- To compare the safety of TAF 25 mg QD versus TDF 300 mg QD as determined by the change from baseline in serum creatinine at Week 48

Other secondary objectives of this study are as follows:

- To compare the efficacy of TAF 25 mg QD versus TDF 300 mg QD for the treatment of HBeAg-negative, chronic hepatitis B in regard to the proportion of subjects with plasma HBV DNA levels below 29 IU/mL at Weeks 96 and 144
- To compare the efficacy of TAF 25 mg QD versus TDF 300 mg QD for the treatment of HBeAg-negative, chronic hepatitis B in regard to the proportion of subjects with plasma HBV DNA levels below 29 IU/mL (target not detected) at Weeks 48, 96, and 144
- To compare the biochemical (ALT normalization by central laboratory and AASLD criteria) response of TAF 25 mg QD versus TDF 300 mg QD for the treatment of HBeAg-negative, chronic hepatitis B at Weeks 48, 96, and 144
- To compare the serological response (loss of HBsAg with seroconversion to anti-HBs) of TAF 25 mg QD versus TDF 300 mg QD for the treatment of HBeAg-negative, chronic hepatitis B at Weeks 48, 96, and 144
- To compare the change in fibrosis as assessed by FibroTest[®] of TAF 25 mg QD versus TDF 300 mg QD for the treatment of HBeAg-negative, chronic hepatitis B at Weeks 48, 96, and 144

- To compare the incidence of drug resistant mutations of TAF 25 mg QD versus TDF 300 mg QD at Weeks 48, 96, and 144
- To compare the change from baseline in ophthalmologic findings by fundoscopic examination of TAF 25 mg QD versus TDF 300 mg QD at Weeks 24, 48, 72 , 96, and 144 (or ED visit if prior to Week 144 and more than 24 weeks since prior exam) in a subset of subjects

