The duration of double-blind treatment is 144 weeks (96 weeks under Amendments 2.1). At Week 144, all subjects remaining on blinded treatment will be switched to the open-label TAF 25 mg QD extension period for up to an additional 240 weeks (Week 144 through Week 384/ED). Subjects already assigned to open-label TAF 25 mg QD at Week 96 per Amendment 2.1 will continue on open-label TAF 25 mg QD through Week 384/ED. All subjects who complete the double-blind period of treatment are eligible for participation in the open label TAF 25 mg QD extension period. Subjects who permanently discontinue study drug (either prematurely [ED] or at the end of study [Week 384]) for reasons other than HBsAg loss with confirmed seroconversion to anti-HBs, will be followed every 4 weeks for 24 weeks off treatment or until initiation of alternative, commercially available HBV therapy, whichever occurs first.

Subjects with HBsAg loss with confirmed seroconversion to anti-HBs should discontinue study drug within 3-6 months following confirmation of seroconversion to anti-HBs. Subjects with HBsAg loss with confirmed seroconversion to anti-HBs prior to Week 48 are not permitted to discontinue study drug prior to the Week 48 visit. After Week 48, these subjects who discontinue study drug will be followed off treatment every 4 weeks for 12 weeks and then per the study visit schedule ([Appendix 2](#)) through Week 384/ED. Discontinuation of study drug for subjects experiencing HBsAg loss with confirmed seroconversion to anti-HBs, who have known bridging fibrosis or cirrhosis, should be considered on a case by case basis.

Figure 3-1. Study Schema

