- To characterize the pharmacokinetics of TAF and tenofovir (TFV) and determine intracellular concentrations of tenofovir diphosphate (TFV-DP) within peripheral blood mononuclear cells (PBMC) in a subset of subjects receiving TAF or TDF
- To evaluate the comparative open-label efficacy, safety, and incidence of drug resistance mutations of TAF 25 mg QD from Week 144 through Week 384 in subjects initially randomized to TAF 25 mg QD and in subjects sequentially treated with TDF 300 mg QD and then switched to open-label TAF

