8.2. Analysis Conventions

8.2.1. Analysis Sets

8.2.1.1. Efficacy

The primary analysis set for efficacy analysis the Full Analysis Set (FAS), defined as all randomized subjects who receive at least one dose of study drug. Subjects will be analyzed according to the randomized treatment assignment.

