8.5.2. Analyses of Other Endpoints of Interest

Continuous secondary endpoints will be summarized using conventional descriptive statistics (n, mean, standard deviation, median, Q1, Q3, minimum, and maximum) by treatment group and overall. A Wilcoxon rank sum test will be used to compare the treatment groups, in an exploratory manner.

Categorical secondary endpoints will be summarized by number and percentage of subjects that meet the endpoint. A two-sided Mantel-Haenszel test, controlling for the randomization strata, will be used to compare the treatment groups, in an exploratory manner. Missing data will be handled by the missing = failure approach.

For the incidence of drug resistant mutations, the missing = excluded approach will be employed.

An analysis of the China subpopulation will also be conducted when approximately 150 randomized and treated China subjects complete 48 weeks of double-blind treatment or discontinue prematurely to examine the consistency of the responses between the China subpopulation and the overall population.

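### At Week 144 the TAF-versus-TDF efficacy comparison counts subjects switched to open-label TAF at Week 96 (Amendment 2.1) in their randomised arm, so part of the TDF arm has had 48 weeks of TAF

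*Protocol*

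**What the plan says.** **The switch.** Protocol 3.1 gives two blinded durations, 144 weeks and, under Amendment 2.1, 96 weeks. Of the second group it says: "Subjects already assigned to open-label TAF 25 mg QD at Week 96 per Amendment 2.1 will continue on open-label TAF 25 mg QD". The visit schedule treats these subjects as real: Sections 6.3.1.9 and 6.3.1.11 dispense open-label TAF to them at Weeks 108, 120 and 132.

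**The comparison.** Section 2 compares TAF with TDF "in regard to the proportion of subjects with plasma HBV DNA levels below 29 IU/mL at Weeks 96 and 144". It sets Week 144 objectives for undetectable HBV DNA, ALT normalisation, HBsAg response, FibroTest and resistance as well. Section 1.3.2 says durability "at Weeks 96 and 144 will also be assessed in a double blind fashion".

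**The analysis rule.** Section 8.2.1.1: "Subjects will be analyzed according to the randomized treatment assignment". Section 8.5.2, for categorical endpoints: "A two-sided Mantel-Haenszel test, controlling for the randomization strata, will be used to compare the treatment groups, in an exploratory manner". Continuous endpoints get a Wilcoxon test. Neither test is restricted by visit or by regimen.

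**The open-label period.** Section 8.1.1 dates the open-label objective "from Week 144 through Week 384 in subjects initially randomized to TAF 25 mg QD" and in those switched from TDF. Section 2 states the same objective with no start week. SAP 1.1 starts it at Week 96 or Week 144, according to amendment. The Synopsis carries safety summaries on "by original treatment arms (TAF versus TDF) will continue through Week 384".

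**The concern.** A Week 144 durability comparison against TDF needs a control arm that has taken TDF for 144 weeks. Under the stated grouping rule, TDF subjects switched at Week 96 stay in the TDF arm, and nothing in the supplied documents excludes them, ends their data at the switch or shows them separately. They are also no longer on blinded drug, so the description in Section 1.3.2 does not fit them.

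If switched subjects come to resemble the TAF arm, the mixture moves the arms closer together. A small Week 144 difference could then be read as TAF holding up against TDF when part of it is TAF compared with TAF.

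**Working it through.** **1. Exposure at Week 144.** 144 - 96 = 48 weeks of TAF for a subject switched at Week 96. The Week 48 visit comes well before the switch and the Week 96 visit is where it takes place, so neither analysis is affected.

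**2. The plan's own figure.** Protocol 8.8 has 260 TAF and 130 TDF subjects, 91% response in both arms, a 10% margin and one-sided 0.025.
- SE = sqrt(0.91 × 0.09/130 + 0.91 × 0.09/260) = 0.0307
- Power = Φ(0.10/0.0307 - 1.96) = 90.2%, against 90% stated

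The figure reproduces. It is a Week 48 figure; the documents give no margin or power for Week 144.

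**3. Dilution at Week 144.** Let f be the share of the TDF arm switched at Week 96, and assume that switched subjects respond like TAF subjects.
- TDF-arm rate = (1 - f) × p(TDF) + f × p(TAF)
- Expected difference = (1 - f) × [p(TAF) - p(TDF)]

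The documents do not give f, so only a range can be shown. For illustration, take TDF at 91% and TAF at 81%, a true deficit equal to the margin. Reuse the Week 48 margin and sample sizes, although the plan applies neither at Week 144. With m the TDF-arm rate, the chance of meeting the margin is Φ([0.10 - 0.10(1 - f)]/SE - 1.96), where SE = sqrt(m(1 - m)/130 + 0.81 × 0.19/260).

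| f | Expected difference (points) | Chance of wrongly meeting a 10% margin |
|---|---|---|
| 0 | -10 | 2.5% |
| 25% | -7.5 | 9.9% |
| 50% | -5 | 24.9% |
| 75% | -2.5 | 45.4% |
| 100% | 0 | 66.0% |

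**4. Price of restricting the comparison.** Suppose the same share f leaves both arms and both rates are 91%. The standard error is then 0.0307/sqrt(1 - f).

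| f | TAF / TDF subjects | 95% half-width (points) | Power at a 10% margin |
|---|---|---|---|
| 0 | 260 / 130 | 6.0 | 90.2% |
| 25% | 195 / 97.5 | 7.0 | 80.4% |
| 50% | 130 / 65 | 8.5 | 63.3% |
| 75% | 65 / 32.5 | 12.1 | 36.9% |

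At f = 100% no Week 144 comparison with TDF is possible.

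**The case against.** **The test is exploratory.** Section 8.5.2 says so, and no alpha or margin is attached to Week 144. This stands and limits the consequence: no confirmatory claim is at risk.

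**The Week 144 handling is inferred.** The supplied SAP covers only the Week 48 analysis of China subjects (SAP 1 and 2) and summarises no secondary efficacy endpoint beyond Week 96 (SAP 6.2.1). No SAP for the non-China subjects was supplied. Within its scope this SAP separates the phases: summaries are confined to the double-blind phase (SAP 6 and 7), laboratory abnormalities restart from an open-label baseline (7.2.2.1), and BMD counts only to Open-label Study Day 14 (7.3.1). That is a good precedent, but it does not govern Week 144, where the protocol's own rule leads to the mixed arm.

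**Analysis by randomised arm is legitimate.** It is, for the effect of assignment to either sequence. It does not answer the stated question of double-blind durability against TDF.

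**Restriction may not preserve randomisation.** No passage says that amendment status is unrelated to arm, and SAP 1.2 refers to subjects who consented to Amendment 3.1 later. This stands; the subset needs a definition that does not depend on consent or persistence, and a balance check.

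**Stronger readings to avoid.** A reader might infer that Week 144 bone and renal differences will be masked by a calculable amount. The documents do not support that. The BMD and creatinine planning differences are Week 48 values (8.8) for Week 48 endpoints (8.1.3). This protocol performs DXA only at capable China sites, and SAP 1.2 (Study Duration) puts all China subjects on three years of blinded drug. Protocol 3.1 and 4.1 give China 96 weeks and 5.3 gives 144; those passages must be reconciled.

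A reader might also infer that Weeks 240 and 384 carry a false test against TDF. Section 1.3.2 already describes those groups as treatment sequences, and the TAF-versus-TDF objectives in Section 2 end at Week 144. That part is mainly labelling.

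**Conclusion.** The concern holds for the Week 144 efficacy comparison in subjects treated under Amendment 2.1, who on SAP 1.2 are non-China subjects. Followed as written, the protocol counts subjects with 96 weeks of TDF and 48 weeks of TAF as TDF, in a comparison it describes as double blind. The expected difference is about (1 - f) of its true value to the extent that switched subjects respond like TAF subjects. Both f and that response are unknown from the documents, so the tables above are a range under assumptions and not an estimate. If the arms truly do not differ, nothing is diluted, but the analysis still could not show that.

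The open-label objective covers the switched sequence in Section 2 and SAP 1.1; only the Week 144 start in Protocol 8.1.1 is out of line. This is worth correcting before the Week 144 analysis and gives no reason to doubt the Week 48 or Week 96 results.

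**What to change.** In Protocol 8.5.2 and 8.6, and in the SAP that will govern Week 144:

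1. Make the Week 144 TAF-versus-TDF comparison in subjects whose planned blinded period is 144 weeks. Define this identically in both arms by the amendment in force at the Week 96 visit (the scheduled date for anyone who stopped earlier), not by who stayed on drug or by later individual consent.
2. Take Week-96-switch subjects of both arms out of that comparison's denominator, so that missing = failure does not turn them into failures. End their blinded TAF-versus-TDF data at the first open-label dose.
3. Show them separately as TAF-TAF and TDF-TAF. Report f and baseline balance by arm in the restricted set.
4. Keep the all-randomised analysis as supportive.
5. Align the open-label objective in Protocol 8.1.1 with Section 2 and SAP 1.1, so that it starts at each subject's own switch (Week 96 or Week 144).
6. Label Week 240 and Week 384 results TAF-TAF versus TDF-TAF.

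This needs wording and programming only, with no new data. The cost is a smaller Week 144 sample and a wider interval: at f = 50% the half-width grows from 6.0 to 8.5 points under the Week 48 planning rates.

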3.2. Biomarker Testing

3.2.1. Biomarker Samples to Address the Study Objectives:

The following biological specimens will be collected in this study and will be used to evaluate the association of exploratory systemic and/or tissue specific biomarkers with study drug response, including efficacy and/or adverse events and to increase knowledge and understanding of the biology of chronic hepatitis B. The specific analyses will include, but will not be limited to, the biomarkers and assays listed below. Because biomarker science is a rapidly evolving area

of investigation, and adverse events in particular are difficult to predict, it is not possible to specify prospectively all tests that will be done on the specimens provided. The testing outlined below is based upon the current state of scientific knowledge. It may be modified during or after the end of the study to remove tests no longer indicated and/or to add new tests based upon the growing state of art knowledge.

- Blood sample for bone biomarkers – including, but not limited to, C-type collagen sequence (CTX) and procollagen type 1 N-terminal propeptide (P1NP)
- Urine sample for renal biomarkers – including, but not limited to, retinol binding protein and beta-2-microglobulin

These specimens will be collected from all subjects in a fasted state.

3.2.2. Biomarker Samples for Optional Pharmacogenomic Research

A separate, specific consent form will be required to document a subject's agreement to provide additional samples for optional pharmacogenomic research. From subjects who agree to participate and provide their additional specific consent, a blood sample will be obtained. This sample should be collected at the Baseline visit, prior to the first dose of study drug, but may be collected at any time during the study or at a separate unscheduled study visit, if necessary. The specimens collected for optional pharmacogenomic research will be used to identify or validate genetic markers that may increase our knowledge and understanding of the biology of the study disease and related diseases and to study the association of genetic markers with disease pathogenesis, progression and/or treatment outcomes, including efficacy, adverse events, and the processes of drug absorption and disposition. These specimens may be used also to develop biomarker or diagnostic assays and establish the performance characteristics of these assays. The collection and analysis of optional future research specimens will facilitate the rational design of new pharmaceutical agents and the development of diagnostic tests, which may allow for individualized drug therapy for subjects in the future.

3.3. Intensive PK Substudy (Optional)

For subjects who provide a separate informed consent (n=16 and up to n=32), an intensive pharmacokinetic substudy will be performed once at either of the Week 4, 8 or 12 visits, at select sites to assess intensive PK profiling in plasma.

Subjects participating in the PK substudy (at sites which can process PBMCs) will also be asked to provide a PBMC (pre-dose) sample at the intensive PK substudy visit. This will be used to evaluate PBMC concentrations of tenofovir diphosphate (TFV-DP), the active form of tenofovir (TFV).

3.4. Ophthalmologic Substudy (Optional)

For subjects who provide a separate informed consent ($n = 30$), a substudy will be conducted to assess ophthalmologic findings, including fundoscopic examination with retinal photographs (both eyes), anytime during the screening period, and must be completed prior to the first dose of study drug, and at Weeks 24, 48, 72, 96 and 144/ visits at select sites. An exam should be performed at the ED visit if prior to Week 144 and not done within the past 24 weeks.

An examination of the full retinal field should be conducted noting changes or abnormalities. Photographs of the retina must be taken at each exam and filed in the subject's source medical records. A central vendor will be used to assess the retinal photographs.

4. SUBJECT POPULATION

4.1. Number of Subjects and Subject Selection

Approximately 390 subjects, who are 18 years of age and older, with HBeAg-negative chronic hepatitis B will be randomized 2:1 to receive either blinded TAF 25 mg and TDF 300 mg matched placebo (n = 260) or TDF 300 mg and TAF 25 mg matched placebo (n = 130) for 144 weeks (96 weeks under Amendment 2.1).

For China, approximately 150 subjects, who are 18 years of age and older, with HBeAg-negative chronic hepatitis B will be randomized 2:1 to receive either blinded TAF 25 mg and TDF 300 mg matched placebo (n = 100) or TDF 300 mg and TAF 25 mg matched placebo (n = 50) for 96 weeks.

4.2. Inclusion Criteria

Subjects must meet all of the following inclusion criteria to be eligible for participation in this study.

1. Must have the ability to understand and sign a written informed consent form, which must be obtained prior to initiation of study procedures.
2. Male and non-pregnant, non-lactating female subjects, 18 years of age and older, based on the date of the screening visit. A negative serum pregnancy test at Screening is required for female subjects of childbearing potential (as defined in [Appendix 6](#)).
3. Documented evidence of chronic HBV infection (e.g. HBsAg positive for more than 6 months).
4. HBeAg-negative, chronic hepatitis B with all of the following:
 - HBeAg-negative and HBeAb-positive at Screening (if the subject is deemed ineligible for this study by HBV serology [i.e. HBeAg-positive CHB], this information may be used to determine eligibility for GS-US-320-0110 [another Gilead Sciences Phase 3 study in HBeAg-positive, CHB subjects; this study must also be IRB/EC approved at the participating center])
 - Screening HBV DNA $\geq 2 \times 10^4$ IU/mL
 - Screening serum ALT level > 60 U/L (males) or > 38 U/L (females) and $\leq 10 \times$ ULN (by central laboratory range)

5. Treatment-naïve subjects (defined as < 12 weeks of oral antiviral treatment with any nucleoside or nucleotide analogue), **OR** treatment-experienced subjects (defined as subjects meeting all entry criteria [including HBV DNA and serum ALT criteria] and with ≥ 12 weeks of previous treatment with any nucleoside or nucleotide analogue) will be eligible for enrollment. Treatment-experienced subjects receiving oral antiviral treatment at Screening must continue their treatment regimen until the time of randomization, when it will be discontinued.
6. Any previous treatment with interferon (pegylated or non-pegylated) must have ended at least 6 months prior to the baseline visit.
7. Estimated creatinine clearance (CL_{Cr}) ≥ 50 mL/min (using the Cockcroft-Gault method) based on serum creatinine and actual body weight as measured at the Screening evaluation, as follows:

$$\frac{(140 - \text{age in years}) (\text{body weight [kg]})}{(72) (\text{serum creatinine [mg/dL]})}$$

[Note: multiply estimated rate by 0.85 for women]

8. Normal ECG (or if abnormal, determined by the investigator not to be clinically significant)
9. Must be willing and able to comply with all study requirements.

